4.5.3.2 Incidence and summary of ARIA

Incidence of ARIA-E, ARIA-H, ARIA-E and ARIA-H (not necessarily concurrent), concurrent ARIA-E and ARIA-H, ARIA-E or ARIA-H, isolated ARIA-H (only ARIA-H, no ARIA-E), ARIA-H microhemorrhage, ARIA-H macrohemorrhage and ARIA-H superficial siderosis will be summarized based on both AE eCRF and MRI data. If there is any discrepancy in incidence between the two data sources, a listing of the subjects and ARIA events with discrepancy will be provided. In addition, the incidence table based on AE eCRF source will also be done by treatment group (placebo, low dose, high dose and BIIB037 total; analysis display A in Appendix 6.1).

Number of subjects with each type of ARIA, maximum severity and worst symptomatic status of the type of ARIA being analyzed will be summarized based on AE eCRF. For subjects with symptomatic ARIA, the maximum severity of symptoms will also be summarized.

Number of subjects with ARIA-H microhemorrhage events post-baseline (broken down by categories of 1-4, 5-9 and ≥ 10) stratified by whether they have had microhemorrhage at baseline will be summarized based on safety MRI data. The summary will be conducted based on the MRI that shows the maximum number of microhemorrhages as well as the last MRI in the study period.

Summary of concurrent ARIA-E and ARIA-H will be provided including the following information: number of subjects with concurrent ARIA-E and ARIA-H (and further broken down to each type of ARIA-H), the severity of ARIA-E based on MRI, the symptomatic status of ARIA-E, the severity of symptoms based on AE eCRF. For subjects with recurrent ARIA-E events, if there is an event concurrent with ARIA-H, it will be used for the summary, and the first concurrent event will be used if there are more than one event concurrent with ARIA-H.

An incidence table of AEs considered by the investigator to be related to ARIA by system organ class and preferred term for subjects with symptomatic ARIA will be provided, as well as a listing of these AEs. Similarly, an incidence table of AEs related to ARIA for subjects with symptomatic ARIA and severe symptoms will be provided, as well as a listing of these AEs.

Listings of AE records for each type of ARIA events and listings of MRI assessments for subjects with each type of ARIA events will be provided.

Montreal Cognitive Assessment (MOCA) is performed at baseline and at each unscheduled ARIA monitoring visit for ARIA subjects (approximately every 4 weeks) except for mild asymptomatic microhemorrhage subjects. An incidence table of subjects with ARIA events whose MOCA total scores decrease 2 points or more from baseline will be provided. A listing of MRI assessments and MOCA total scores for subjects with ARIA events will be provided.

Line plots of MMSE mean change from baseline values and standard errors at each planned visit (baseline, Week 26, Week 50 and Week 78) will be provided by treatment group stratified by ApoE status and with stratification on the following factors:

- (1) ARIA-E severity based on MRI. The groups are: subjects without ARIA-E, subjects with mild ARIA-E, subjects with moderate ARIA-E and subjects with severe ARIA-E.

- (2) Within ARIA-E subjects, stratify by the severity of the concurrent symptoms based on AE eCRF. The groups are: subjects without symptoms, subjects with mild symptoms, subjects with moderate symptoms, and subjects with severe symptoms.

For subjects with recurrent ARIA-E events, the first ARIA-E event will be used for the classification for each of the factors.

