ARIA-H superficial siderosis	Asymptomatic ARIA-H (Superficial Siderosis) Symptomatic ARIA-H (Superficial Siderosis)	superficial siderosis of the central nervous system	superficial siderosis of the central nervous system

For any specific ARIA event, the start date of the duration based on MRI is the date of the MRI assessment that initially identifies the ARIA event, and the end date of the duration based on MRI is the date of the MRI assessment that shows the complete resolution of this ARIA event (in the case of ARIA-E), or the date of the MRI assessment that shows ARIA being stable (in the case of ARIA-H). Stable was defined as ‘No change’ or ‘decrease’ in number, size, severity or number of locations between 2 consecutive MRIs including the initial detection MRI and the follow-up MRIs.

For symptomatic ARIA events, if there is any related symptom that proceeds the first MRI identification, then the symptom onset date will be used as the start date of the symptomatic ARIA duration. The end date of the symptomatic ARIA duration will be the date of the resolution or stable MRI as defined above for the duration based on MRI.

If the severity increases, or the event changes from asymptomatic to symptomatic, or from non-serious to serious, more than one AE records will be added to eCRF to capture the change with new start/end AE dates (the end date of the previous record will be the start date of the next record). For analysis, records with changes in severity or symptomatic status or seriousness are considered as a single ARIA event. The severity/symptomatic status/seriousness for that event is defined as the worst level among all the AE records that belong to that event.

If the same type of ARIA event happens again after the previous event has ended, then it is considered a recurrent event of ARIA of that type. Recurrent events will be referred as the second event, the third event, and etc.

If the duration based on MRI of an ARIA-E event overlaps with the duration based on MRI of an ARIA-H event, then these 2 ARIA events are considered as concurrent events.

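### The concurrent ARIA-E/ARIA-H summary grades a subject on the first concurrent event only, so it can understate the worst severity and symptoms reached during concurrent ARIA

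*SAP*

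**What the plan says.** SAP 4.5.3.2 specifies the content of the concurrent summary as "number of subjects with concurrent ARIA-E and ARIA-H (and further broken down to each type of ARIA-H), the severity of ARIA-E based on MRI", followed by the symptomatic status of ARIA-E and the severity of symptoms. It then says which event represents a subject who has had ARIA-E more than once. A concurrent event takes precedence over one that is not concurrent, and where several are concurrent the earliest is taken: "the first concurrent event will be used if there are more than one event concurrent with ARIA-H". LTE SAP 3.5.3.2 carries the same rule into the LTE period and the combined active-treatment period.

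Earlier in 4.5.3.2, the grading for each ARIA type taken alone is by worst level: "Number of subjects with each type of ARIA, maximum severity and worst symptomatic status of the type of ARIA being analyzed will be summarized", and "For subjects with symptomatic ARIA, the maximum severity of symptoms will also be summarized". SAP 4.5.3.1 also takes the worst level within a single event: "The severity/symptomatic status/seriousness for that event is defined as the worst level among all the AE records that belong to that event".

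**The concern.** ARIA is the adverse event of special interest, and the plan gives edema overlapping with hemorrhage its own summary. A reader will take the severity and symptom rows of that summary as showing how bad concurrent ARIA became. Under the rule, a subject whose first concurrent event is mild and asymptomatic keeps that row even if a second concurrent event is severe and symptomatic. The same subject could then appear as severe in the ARIA-E maximum-severity table and as mild in the concurrent table, and the SAP gives no reason for the difference. Against the worst concurrent event, the first event can be equal or milder but never worse, so the discrepancy has one direction.

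**Working it through.** The SAP states no ARIA rate, so there is no figure of its own to reproduce. The check is a reading of the sections, followed by an illustration on assumed inputs.

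**1. Who is affected.** The rule bites only for subjects with at least two ARIA-E events that each overlap an ARIA-H event on MRI-based duration. SAP 4.5.3.1 ends an ARIA-H event when MRI shows it stable, so a second ARIA-E is concurrent again only if there is new or not-yet-stable ARIA-H. Worsening within one event is already taken at its worst level.

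**2. Which cells are affected.** The count of subjects with concurrent ARIA does not change, since one concurrent event is enough to enter it. The rows for ARIA-E MRI severity, symptomatic status and symptom severity can change. Whether the breakdown by ARIA-H type changes is unclear: the rule selects among ARIA-E events, and the text does not say whether it also governs that breakdown.

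**3. Whether another output supplies the result.**

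| Planned output | Captures later, worse events? | Gives severity or symptoms jointly with concurrency? |
|---|---|---|
| Maximum severity, worst symptomatic status and maximum symptom severity by ARIA type (4.5.3.2) | Yes | No |
| Incidence of each ARIA-H type and of concurrent ARIA, from eCRF and MRI (4.5.3.2) | Yes, as counts | No |
| MRI severity of every ARIA-E event; symptom severity of every symptomatic one (4.5.3.3) | Yes | No |
| Second and third ARIA-E event tables (4.5.3.3) | Yes | No |
| Listings of AE records and MRI assessments by ARIA type (4.5.3.2) | Yes | Only if overlaps are rebuilt by hand |

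The concurrent summary is the only planned table with the joint result, and for subjects with several concurrent events it gives that result for the first event only.

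**4. Illustration of size.** Assumed inputs, none from the SAP:
- r = share of concurrent-ARIA subjects with exactly one further concurrent event (5% to 30%).
- p = probability that a concurrent event has the worst feature of interest, for example severe symptoms (2% to 20%), independent between events.

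Formulas:
- Counted under the first-event rule: p.
- Having the feature at any concurrent event: (1 − r)p + r[1 − (1 − p)²].
- Share missed: 1 − (first ÷ any).

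Worked case, r = 0.20 and p = 0.05: any = 0.80 × 0.05 + 0.20 × (1 − 0.95²) = 0.0400 + 0.0195 = 0.0595. The table shows 5.0% against 5.95%, a gap of 0.95 percentage points of concurrent-ARIA subjects. Share missed = 1 − 0.0500/0.0595 = 16.0%.

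Share missed over the grid:

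| r | p = 2% | p = 5% | p = 10% | p = 20% |
|---|---|---|---|---|
| 5% | 4.7% | 4.5% | 4.3% | 3.8% |
| 10% | 8.9% | 8.7% | 8.3% | 7.4% |
| 20% | 16.4% | 16.0% | 15.3% | 13.8% |
| 30% | 22.7% | 22.2% | 21.3% | 19.4% |

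The loss is larger if later events tend to be worse, and smaller if a subject's events tend to resemble each other. Whatever the dependence, the number of misgraded subjects cannot exceed the number with two or more concurrent events.

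**The case against.** The strongest defence is that choosing the first or the worst event is a choice between two valid descriptive summaries. The table carries no test and no decision rule. The first-event rule ties severity, symptoms and concurrency to one real episode, whereas taking the worst of each feature separately can assemble a profile that never occurred. First-event classification is also used elsewhere: the MMSE line plots in 4.5.3.2 group subjects by their first ARIA-E event, and 4.5.3.3 has a full table of first ARIA-E events. This all stands, and it is a reason to keep the first-event rows. It does not remove the gap, because the plots are not a severity count and the first-ARIA-E table does not show concurrency. Nor can that table stand in for the first-concurrent-event rows, since a subject's first concurrent event need not be the first ARIA-E event.

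A reader might infer three stronger things that the SAP does not support:

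- *That rare worst outcomes are undercounted across the ARIA analysis.* They are not. The tables set out above capture later episodes, and the gap lies in one joint table.
- *That later macrohemorrhages are lost.* The plan separately states that "ARIA-H microhemorrhage, ARIA-H macrohemorrhage and ARIA-H superficial siderosis will be summarized based on both AE eCRF and MRI data", with no first-event rule. Within the concurrent table, the wording leaves open whether the type breakdown is limited to the first event, so this is possible but not established.
- *That arms with more ARIA-E are the most understated.* In the illustration, the share missed depends on r and p and not on how common ARIA-E is, and the SAP gives no r by arm.

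**Conclusion.** The point holds for the concurrent ARIA-E/ARIA-H summary in SAP 4.5.3.2 and LTE SAP 3.5.3.2. For subjects with two or more concurrent ARIA-E events, that table can understate the worst ARIA-E MRI severity, symptomatic status and symptom severity reached during concurrent ARIA, and compared with the worst concurrent event it cannot overstate them. The size cannot be derived from the SAP. The illustrative 4% to 23% is a share of the subjects who have the worst feature at some concurrent event, not of all subjects or of all ARIA cases, and it rests entirely on the assumed r, p and independence between events. The LTE and combined analyses allow more time for recurrence, but nothing in the SAP quantifies this. It is a cheap improvement to a descriptive safety table and does not bear on the validity of the wider ARIA analysis.

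**What to change.** In SAP 4.5.3.2 and LTE SAP 3.5.3.2, keep the rows based on the first concurrent event and add text along these lines:

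> For subjects with more than one ARIA-E event concurrent with ARIA-H, the table will also present the worst ARIA-E MRI severity, the worst symptomatic status and the worst symptom severity across all concurrent events. A footnote will state that these values may come from different episodes. In the breakdown by ARIA-H type, a subject will be counted under each type that was concurrent with any ARIA-E event.

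The last sentence also settles the unclear scope of the type breakdown; type counts may then add to more than the number of subjects, which the footnote should mention. Adding rows rather than replacing the rule preserves the first-concurrent-event detail, which no other table gives. The cost is a few extra table rows and one programming rule in each of the two plans. No new data are needed.

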4.5.3.3 Summary of recurrent ARIA-E

Follow-up adjusted incidence rate of subjects with ARIA-E, with 2 or more events of ARIA-E, with 3 or more events of ARIA-E and with more than 3 events of ARIA-E based on their entire follow-up time will be summarized based on AE eCRF. The entire follow-up time is from the first dose until the last day in the placebo-controlled period.

Number of total ARIA-E events and the MRI severity of each event will be summarized based on AE eCRF. Number of total symptomatic ARIA-E events, the MRI severity of each symptomatic event and the severity of the symptoms of each symptomatic event will be summarized based on AE eCRF.

Summary of first ARIA-E events table based on AE eCRF will summarize the number of subjects with a first event of ARIA-E, the MRI severity of the events, the symptomatic status of the events, the severity of the symptoms for symptomatic events, whether SAE or not, number of resolved and unresolved events, duration of the resolved events, time from first infusion in study (active or placebo) to onset, number of doses received since the start of the study to onset, dose level of the last infusion received prior to onset, dosing status (continue as planned, dose interrupted, dose reduced, or dose discontinued) after the events, and the number of subjects with recurrent ARIA-E events. The same summary of first ARIA-E events table will also be done on subjects who had recurrent ARIA-E events.

Summary of recurrent ARIA-E events table based on AE eCRF will summarize the following information for both the second and third event of ARIA-E events: the number of subjects with the previous event of ARIA-E, the number of subjects with at least one dose and one MRI after the previous ARIA-E resolution, the number of subjects with this event of ARIA-E, the MRI severity of the events, the symptomatic status of the events, the severity of the symptoms for symptomatic events, whether SAE or not, number of resolved and unresolved events, duration of the resolved events, time from first infusion in study (active or placebo) to onset, time from previous resolution to onset, number of doses received since the start of the study to onset, dose level of the last infusion received prior to onset, dosing status (continue as planned, dose interrupted, dose reduced, or dose discontinued) after the events. The number of subjects with more than 3 events of ARIA-E, and the number of subjects who discontinued study treatment after recurrent ARIA-E onset will also be summarized.

A listing of subjects who withdrew from the study with unresolved ARIA-E or subjects with ongoing ARIA-E at the time of data cutoff (also considered as unresolved) will be provided with the details of the event including the duration from onset to last follow-up.

For subjects with recurrent ARIA-E, a listing of study drug administration, MRI assessments, severity and symptomatic status of each event, and end-of-treatment reason (if present) will be provided.

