The total duration of study participation for each subject only participating in the placebo-controlled period of the study will be up to approximately 102 weeks, including a series of Screening visits within 8 weeks before administration of the first dose, a 76-week placebo-controlled treatment period, and a safety follow-up (FU) period of approximately 18 weeks after the final dose. The total duration of study participation for each subject participating in the placebo-controlled period and the LTE period will vary and be up to approximately 362 weeks, including a series of Screening visits within 8 weeks before administration of the first dose, a 76-week placebo-controlled treatment period, a 4-week FU period, a 256-week aducanumab dose-blind treatment period, and a safety FU period of approximately 18 weeks after the final dose.

Investigators, study site staff (except for the designated unblinded pharmacist/technician), and study subjects will be blinded to the subjects' randomized treatment assignment for the placebo-controlled period. During the LTE period, investigators and subjects will remain blinded to the treatment assignment in the placebo-controlled period and the aducanumab dose for the LTE period.

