3 SAMPLE SIZE JUSTIFICATION

The study's sample size is based, in part, on results from a protocol-specified interim analysis from Study 221AD103 which included 1 year data from 1, 3 and 10 mg/kg treatment groups.

A sample size of 450 subjects per treatment group (1350 in total) was planned to have approximately 90% power to detect a true mean difference of 0.5 in change from baseline CDR-SB at Week 78 between the 2 treatment groups. This power calculation was based on a 2-sided t-test assuming equal variance with a final significance level of 0.05, a standard deviation (SD) of 1.92 and a drop-out rate of 30%. The SD estimate of 1.92 for Week 78 reflected a 39% increase over the SD from the protocol-specified interim analysis of 1-year data.

The assumed true mean difference of 0.5 between the 2 treatment groups represents an approximately 25% reduction in the placebo mean change from baseline at Week 78 if the placebo mean change is estimated to be 2.

As defined in the protocol, the sample size for this study (and for the identically designed Study 221AD301) was reassessed in a blinded manner in November 2017 (approximately 3 months before enrollment completion and with about 10.6% of the data available on the primary endpoint from Studies 221AD301 and 221AD302 combined). At this timepoint, the SD of the primary endpoint was estimated based on the pooled blinded data from two studies using a modified version of Gould-Shih simple-adjustment one sample variance (Zucker et al. 1999):

$$s_{adj}^2 = s_{os}^2 - \frac{2N}{9(N-1)} \delta^2,$$

where N denotes the number of subjects included in the analysis for blinded sample size re-estimation (subjects with both baseline and Week 78 CDR-SB available at the time of sample size re-estimation), δ is the assumed true treatment effect (same treatment effect assumed for both the high dose group and low dose group in this analysis), and s_{os}^2 is the unadjusted one sample variance of the primary endpoint estimate from the pooled blinded data.

As a result of this analysis, the sample size has been increased from 1350 to 1605 (450 to 535 per treatment group) to assure adequate power for detecting a mean treatment effect of 0.5.

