4.5.3.5 Time to event analysis

Kaplan-Meier plot of time to first ARIA-E event will be produced based on safety MRI data. Time to event is calculated as date of the MRI assessment that initially detects ARIA-E event - date of first infusion (aducanumab or placebo) +1. Censor time for subjects without ARIA-E is calculated as date of last MRI assessment in the placebo-controlled period - date of first infusion (aducanumab or placebo) +1. Estimated proportion with ARIA-E and number of subjects at risk at selected timepoints will also be presented. The plot will be presented by treatment group stratified by ApoE status.

4.5.3.6 Subgroup analysis for protocol version 4

Due to the change in maximal dose from 6 mg/kg to 10 mg/kg for ApoE ϵ 4 carrier high dose group in protocol version 4, not all subjects have had opportunity to receive the protocol specified high dose (6 doses in titration before receive 10mg/kg) in the placebo-controlled period. Incidence of ARIA events and summary of first ARIA-E events tables will be provided for ApoE ϵ 4 carriers who were randomized to the high dose group, stratified by the expected number of doses at 10 mg/kg (categories of 0, 1-6, 7-13, 14, and a total column of having at least one dose) a subject would have received based on the first infusion date and the date consenting to protocol version 4. Randomization treatment groups will be used for this analysis.

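### ARIA-E duration is summarised over resolved events only; a censored summary of time to resolution should stand beside it

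*SAP*

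**What the plan says.** Section 4.5.3.1 of the placebo-controlled SAP fixes when an ARIA-E event ends: "the end date of the duration based on MRI is the date of the MRI assessment that shows the complete resolution of this ARIA event". An event whose resolving scan has not been seen has no end date.

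Section 4.5.3.3 describes one table for first events and one for second and third events. Each reports, among other items, "number of resolved and unresolved events, duration of the resolved events". The same section plans a listing of subjects who withdrew with the event open and of "subjects with ongoing ARIA-E at the time of data cutoff (also considered as unresolved"; it "will be provided with the details of the event including the duration from onset to last follow-up". Section 3.5.3.3 of the LTE SAP repeats the tables and the listing for the combined active-treatment period.

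A censored-data method is planned for onset only. Section 4.5.3.5 says: "Kaplan-Meier plot of time to first ARIA-E event will be produced based on safety MRI data", with event-free subjects censored at their last MRI. Section 4.2.1 also plans Kaplan-Meier displays for treatment discontinuation and study withdrawal. Neither SAP plans one for time to resolution.

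**The concern.** Duration of an ARIA-E event is a time-to-event quantity, right-censored when the subject leaves or the data are cut before the resolving MRI. Restricting the summary to events seen to resolve conditions on the outcome and selects shorter events.

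It is the only planned duration summary for the adverse event of special interest, so readers are likely to take it as the duration of ARIA-E. Section 4.5.1 displays ARIA tables by dose group and ApoE status, and Section 4.5.3.3 sets first, second and third events alongside one another. The share of open events can differ between those columns. Recurrent events start later and have less remaining time in which resolution can be seen, so a first-versus-recurrent comparison is the most exposed.

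**Working it through.** **No figure to reproduce.** The SAPs state no ARIA-E duration and no expected unresolved share. The direction of the bias can be derived; its size can only be illustrated.

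**Direction.** Let an event last D, and let C be the follow-up available after its onset, independent of D. The event counts as resolved if C ≥ D. With G(d) = P(C ≥ d), the resolved-only mean is E[D·G(D)] / E[G(D)]. G cannot increase with d, so D and G(D) are non-positively correlated and this ratio cannot exceed E[D]. The bias is downward, or nil if every event is seen to resolve.

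**Inputs from the SAP for the follow-up limits.** Section 2.1 gives a 76-week treatment period. Subjects entering the LTE have a 4-week follow-up first (76 + 4 = Week 80). Those who do not enter have "a safety follow-up (FU) period of approximately 18 weeks after the final dose" (76 + 18 = Week 94). Section 3 assumes "a drop-out rate of 30" percent, used below only as an upper value for withdrawal.

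**Illustration 1 (assumed: exponential duration, resolution seen at the next four-weekly MRI, follow-up to Week 80).** Early onset is 4 weeks plus an exponential with mean 24 weeks, capped at Week 75. Even onset is uniform on Weeks 4–76.

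| Underlying mean, onset | Unresolved | Mean, all events (weeks) | Mean, resolved only (weeks) | Shortfall |
|---|---|---|---|---|
| 12 weeks, early | 7.5% | 14.1 | 13.0 | 1 − 13.0/14.1 = 7.8% |
| 12 weeks, even | 14.1% | 14.1 | 11.8 | 1 − 11.8/14.1 = 16.3% |
| 20 weeks, early | 14.3% | 22.1 | 17.8 | 1 − 17.8/22.1 = 19.5% |
| 20 weeks, even | 24.4% | 22.1 | 15.6 | 1 − 15.6/22.1 = 29.4% |

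A Kaplan-Meier median recovered the all-event median in all four rows (12, 12, 16 and 16 weeks).

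**Sensitivity to follow-up and shape.**
- Extending follow-up to Week 94 cuts the shortfall to about 5% (12 weeks, early), 9% (12 weeks, even) and 21% (20 weeks, even).
- Replacing the exponential by a log-normal (log-SD 0.6) with about the same mean as the 12-week rows (14.0 weeks), with follow-up to Week 80, gives about 3% (early) and 7% (even).

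**Illustration 2 (assumed: log-normal duration, median 8 to 24 weeks, log-SD 0.6, four-weekly MRI, onset uniform on Weeks 8–40 or 8–76, follow-up to Week 78 or 94, withdrawal after onset 0% or 30% per 78 weeks).** The unresolved share ran from about 0% to 47%. The shortfall ran from under 1% (11.5 v 11.6 weeks) to 1 − 23.1/30.7 = 24.8%. The Kaplan-Meier median stayed within one four-week MRI step of the all-event median throughout.

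**Effect of late onset.** In Illustration 2, take median 12 weeks, follow-up to Week 78 and no withdrawal. Onset on Weeks 8–40 leaves 1.1% unresolved and the mean reads 15.9 against 16.4 weeks (1 − 15.9/16.4 = 3.0% short). Onset on Weeks 8–76 leaves 21.0% unresolved and it reads 14.7 against 16.4 weeks (1 − 14.7/16.4 = 10.4% short).

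**The case against.** The plan labels the statistic for what it is, counts resolved and unresolved events in the same table, and lists every open event with its time from onset. Open events are outside one summary line, not outside the report. This stands: the figure is correct as labelled and misleads only if read as ARIA-E duration in general.

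Three stronger readings are tempting, and the documents do not support them.

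- **That the open events are the longest ones.** An event also counts as unresolved because the subject withdrew or because it began shortly before cutoff. In Illustration 2, up to 69% of unresolved events had an observed duration below the resolved-only median. What holds is that longer events are preferentially excluded.
- **That the shortfall equals the unresolved share.** With exponential durations this also needs exponential censoring. In the table above, 14.3% unresolved goes with a 19.5% shortfall.
- **That the median drops from 12 to 8 weeks.** This appears in the 12-week rows but is mostly an effect of the four-week grid. With an exponential mean of 12 weeks, 1 − exp(−8/12) = 48.7% of all events resolve by 8 weeks, so a shift of about 1.3 points moves the median a full step. In the early-onset row the resolved-only share is 51.3%. With follow-up to Week 94 that row's median stays at 12 weeks.

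The Week 80 limit is also an assumption: the SAP ties unresolved status to withdrawal or data cutoff, and LTE follow-up runs much longer. Finally, the tables are descriptive and no test of duration is planned. Kaplan-Meier has its own weakness: if subjects withdraw because of an ARIA-E event, the censoring may be informative.

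**Conclusion.** The point holds as a modest one. The only planned summary of ARIA-E duration conditions on resolution, which biases it downward as an estimate of duration in general and can do so unequally across columns and event order. The size cannot be computed from the SAPs. It is negligible if nearly all events resolve, and roughly 3% to 30% on the mean under the illustrative assumptions (follow-up to Week 80 or 94, exponential or log-normal durations, four-weekly MRI). The upper end needs long events, evenly spread onset and follow-up ending at Week 80. Nothing here touches the primary analysis, type I error, ARIA incidence or the time-to-onset analysis.

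**What to change.** In Section 4.5.3.3 of the placebo-controlled SAP and Section 3.5.3.3 of the LTE SAP, keep the resolved-only line. Beside it, add a Kaplan-Meier summary (median and quartiles) of time from onset to resolution, separately for first, second and third ARIA-E events and in the same columns. Include all ARIA-E events, use the same onset date as the existing duration line, and censor unresolved events at the last MRI. Footnote that the estimate relies on non-informative censoring, and that the listing of open events should be read with it.

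The cost is a sentence in each SAP and one extra standard analysis. The dates are already needed for the planned listing, and the method is already used for time to first ARIA-E. Estimates will be imprecise, and some quartiles may not be reached, where recurrent events are few.
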